### **2.2 Secondary Objectives**

1. Analyze IMPACT module and subscale scores across baseline sociodemographic, injury, and treatment variables in order to understand which factors influence QOL.
2. Analyze the reliability of each IMPACT module and subscales.
3. Determine the sensitivity to change for IMPACT modules and subscales.
4. Calculate the minimally clinically important difference (MCID) for each IMPACT module and subscales.

---

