#### 6.4.1 Baseline Data

The following chart review variables will be abstracted after informed consent is obtained and the initial survey is completed. This data will be summarized descriptively with average, median, range, interquartile range, and standard deviation, as appropriate. Each variable will then be tested for association with IMPACT scores on univariable analysis. Clinically or statistically significant variables will then be included in subsequent multivariable testing.

---

---

- Sociodemographic data: Age, sex, race, ethnicity, marital status, smoking status, payor type (private, medicare, Medicaid, government, none / self-pay, or other), and Social vulnerability index (SVI) values based on home address.
  - SVI: A measure of social vulnerability assigned to each zip code or census tract by the Center for Disease Control and Prevention.
- Trauma data: Mechanism, concomitant multisystem trauma, airway status, level of care (discharged from emergencet room, floor/stepdown admit, intensive care admit), presenting signs or symptoms (cranial nerve weakness, trismus, malocclusion, visual impairment), description of facial trauma, comprehensive facial injury (CFI) score, and Facial Injury Severity Score (FISS).
  - CFI: An objective scale based on maxillofacial imaging and clinical exam providing an integer that represents fracture severity by correlating it with the operative time for repairing each fracture.
  - FISS: An objective scale based on maxillofacial imaging and clinical exam providing an interger that represents the objective severity of facial trauma by correlation with the cost of management.
- Management data: Treatment (observation, bedside intervention, or surgical repair), type of surgical repair (closed reduction, open reduction, internal fixation, external fixation, and maxillomandibular fixation [MMF]), hospital length of stay (days), disposition (home versus medical facility)
- Objective complications: Wound infection or dehiscence, Malunion or nonunion, hardware extrusion, or any unplanned return to the emergency department, admission or reoperation related to the facial injury.
- Survey metadata: time from trauma to survey (days), time from intervention to survey (if applicable; days), presence of maxillomandibular fixation at the time of the survey.

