#### **6.4.4 Analysis of Secondary Outcomes of Interest**

1. IMPACT independent predictors: This secondary objective will identify independent variables that are associated with IMPACT scores. Multivariable logistic and linear regression models will be developed for categorical and continuous independent variables, respectively, and tested for association with each IMPACT score. Those independently associated with the IMPACT will be reported and factored into the multivariable regression for the primary endpoint.
2. Internal consistency and reliability will be measured by Cronbach alpha testing, item-response theory (IRT), and correlation between initial and followup surveys for patients completing both within one month.
3. The MCID for each module and subscale will be calculated using an anchor-based approach with a single item that addresses each patient's overall satisfaction.

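### Consequences of the injury can enter the same multivariable testing as injury severity and social factors, so the reported adjusted coefficients do not answer which factors influence QOL

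*Protocol*

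**What the plan says.** Secondary objective 1 (Protocol section 2.2) is explanatory: "Analyze IMPACT module and subscale scores across baseline sociodemographic, injury, and treatment variables in order to understand which factors influence QOL".

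Section 6.4.1, headed Baseline Data, lists the candidate variables in five groups:

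- Sociodemographic: "Sociodemographic data: Age, sex, race, ethnicity, marital status, smoking status, payor type", and the Social Vulnerability Index (SVI).
- Trauma: mechanism, multisystem trauma, airway status, level of care, presenting signs, and the CFI and FISS severity scores.
- Management: treatment, type of repair, "hospital length of stay (days), disposition (home versus medical facility").
- Complications: "Objective complications: Wound infection or dehiscence, Malunion or nonunion, hardware extrusion", and unplanned return, admission or reoperation.
- Survey metadata: time from trauma, time from intervention, and whether maxillomandibular fixation (MMF) is in place at the survey.

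Each variable is first tested alone against IMPACT. Then: "Clinically or statistically significant variables will then be included in subsequent multivariable testing". Section 6.4.4 item 1 gives the reporting rule: "Those independently associated with the IMPACT will be reported". The same variables are carried into the regression for the primary endpoint. Neither section separates variables fixed at or before the injury from those that arise after it.

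**The concern.** The listed variables have an order in time. Social circumstances precede the injury, the injury precedes its treatment, and length of stay, disposition and complications come last. Part of the effect of severity or SVI on QOL may run through those later variables. A regression that contains both gives the earlier variable only the part that does not pass through the later ones. That is a legitimate quantity, but it is not the influence of severity or SVI on QOL.

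The protocol itself ties severity to later care. It describes the CFI as built by correlation with operative time, and says that the FISS "represents the objective severity of facial trauma by correlation with the cost of management". Overlap between these scores and the management variables is therefore to be expected.

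At stake is the conclusion for secondary objective 1. Severity or social vulnerability could be left out of the reported predictors because its effect runs through a longer stay or a complication. It could also appear stronger than it is because a helpful treatment has been held constant. The selected set also feeds the adjusted primary analysis.

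**Working it through.** **The plan's own figures.** The protocol gives no effect size or power for the predictor models. Its sample size (section 6.5) reproduces: 150 / 0.30 = 500 recruited, and 500 / (1 − 0.33) = 747, against 750 stated (exactly 750 if nonresponse is one third). So about 150 patients are available for the least common module and about 500 for the general module.

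**Model.** Let S be severity, M one later variable and Y the IMPACT score, all standardised. A higher Y means worse QOL. Path a runs from S to M, path b from M to Y, and path c′ directly from S to Y.

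- Coefficient of S without M: c′ + ab (total effect).
- Coefficient of S with M in the model: c′ (direct part only).
- Standard error of the total effect: √[(1 − (c′ + ab)²) / n].
- Standard error of the adjusted coefficient: √[(1 − R²) / (n(1 − a²))], with R² = c′² + b² + 2abc′.
- Power ≈ Φ(|coefficient| / SE − 1.96), two-sided 5%. The protocol states 0.05 only for the primary correlation, so its use here is assumed.

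All values of a, b and c′ are assumptions, because the documents give none.

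**Illustration: total effect 0.30, half of it mediated.**

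- Without M, n = 150: SE = √(0.91/150) = 0.0779; 0.30/0.0779 = 3.85; power 97%.
- With M, a = 0.5, b = 0.3, c′ = 0.15: R² = 0.1575; SE = √[0.8425/(150 × 0.75)] = 0.0865; 0.15/0.0865 = 1.73; power 41%.
- With M, a = 0.6, b = 0.25, c′ = 0.15: R² = 0.13; SE = √[0.87/(150 × 0.64)] = 0.0952; 0.15/0.0952 = 1.58; power 35%.
- At n = 500 the same formulas give about 100% without M, and 89% and 82% with M.

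**Other assumptions (a = 0.5, n = 150).**

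| Later variable | b | c′ | Without M | With M | With / without | Power without → with |
|---|---|---|---|---|---|---|
| Worsens QOL | 0.2 | 0.20 | 0.30 | 0.20 | 67% | 0.97 → 0.62 |
| Worsens QOL | 0.3 | 0.10 | 0.25 | 0.10 | 40% | 0.89 → 0.21 |
| Worsens QOL, full mediation | 0.4 | 0 | 0.20 | 0 | 0% | 0.71 → 0.05 |
| Improves QOL | −0.2 | 0.35 | 0.25 | 0.35 | 140% | 0.89 → 0.97 |

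Simulation of the second and fourth rows (1,500 runs each) agrees: the mean coefficient goes from 0.251 to 0.101 and from 0.249 to 0.348. With a varied from 0.3 to 0.7, the adjusted coefficient is 0% to 77% of the total in the harmful cases (b from 0.2 to 0.4, c′ from 0 to 0.2) and 121% to 167% in the beneficial case. The sign of the distortion therefore depends on the later variable.

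**The case against.** **A single joint model is not stated.** Section 6.4.4 item 1 speaks of models in the plural, logistic for categorical and linear for continuous independent variables. A reader might infer from section 6.4.1 that everything enters one model. That is a natural reading but not an explicit one. The difficulty survives the split reading: length of stay would still share the continuous model with CFI, FISS and SVI, and disposition and complications would share the categorical model with payor type, race and mechanism.

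**The direction is not fixed.** A reader might conclude that severity and social effects will be understated. The documents do not support that: treatment is among the later variables and may improve QOL, and the adjusted coefficient would then be too large.

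**The crude association is not lost.** It is tempting to say that the study would declare an effect absent. But section 6.4.1 plans univariable tests of every variable, and section 6.4 promises effect sizes with 95% confidence intervals. Those results are unadjusted for age, social factors or time since trauma, so they do not supply the missing quantity, but they limit the harm.

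**The endpoint wording asks for independent predictors.** Section 6.2 does so, and mutual adjustment fits that wording. For treatment, adjustment for severity is also needed to control confounding. This stands, but it leaves section 6.2 at odds with section 2.2, which speaks of influence.

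**This could wait for the SAP.** Detailed model building could. Here, though, the protocol itself states the entry rule and the reporting rule, and together they answer a different question from the objective.

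**Conclusion.** The point holds in a limited form. As written, sections 6.4.1 and 6.4.4 item 1 let severity and social factors be adjusted for their own possible consequences, and those adjusted coefficients do not answer secondary objective 1. The distortion is downward where the later variable worsens QOL and upward where a treatment improves it.

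The documents do not determine its size. The fall in power from about 97% to 35–41% at 150 patients rests wholly on an assumed total standardised effect of 0.30 and an assumed mediated share of one half. It shows what could happen and is not a property of this plan.

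The matter concerns a secondary objective. It reaches the primary endpoint only through the choice of adjustment variables; the stated validity criterion, a Pearson correlation above 0.4 with p < 0.05, is unaffected. Because the change is cheap, it should be made before analysis.

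**What to change.** In sections 6.4.1 and 6.4.4 item 1, replace the common pool with ordered models on the same data, with time from trauma in all of them:

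1. Sociodemographic variables.
2. Plus injury: mechanism, multisystem trauma, presenting signs, CFI/FISS.
3. Plus treatment and type of repair.
4. Plus level of care, length of stay, disposition, complications and MMF at the survey. Use time from intervention only among treated patients.

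Report each variable's effect from the model in which it first enters. Label coefficients of earlier variables in later models as direct-effect or descriptive.

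Three placements matter. Level of care is listed under trauma data but can follow from severity, so it belongs in step 4. Treatment is kept apart from length of stay and disposition, which can follow from it. Airway status should be assigned to a step in advance, according to whether it records the state at presentation or later care.

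Cost: a few more model fits, longer tables and a few sentences of protocol text. No new patients or data are needed.

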## 6 STATISTICAL CONSIDERATIONS

### 6.1 Primary Endpoint

The primary endpoint pertains to the primary objective, determining the validity of each IMPACT module and subscale for measuring QOL in patients with maxillofacial trauma. This will be determined by correlating the IMPACT scores with the corresponding 15D score, controlling for any independent predictors of IMPACT and 15D scores.

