### 6.4 Statistical Methods

All analysis will be performed by the host institution. Effect sizes with 95% confidence intervals (CI) will be provided for every applicable measurement. The analytical plan will be reviewed by professional biostatisticians at the host institution.

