#### 6.4.3 Analysis of Primary Outcome of Interest

This validity of the IMPACT in measuring QOL will be determined by calculating Pearson's r between the score from each IMPACT module and subscale with the 15D QOL survey.

---

---

Each module or subscale will be considered valid if it shows significant ( $p < 0.05$ ) and at least moderately-positive correlation ( $r > 0.4$ ) with the 15D. All independent variables that influence IMPACT scores will be controlled for in a multivariable regression model.

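### Covariates for the predictor models and the adjusted primary regression are screened by univariable significance, score by score, with no multiplicity control or exploratory label stated

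*Protocol*

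**What the plan says.** Section 6.4.1 lists the chart variables and sets a two-step rule. First, "Each variable will then be tested for association with IMPACT scores on univariable analysis". Then, "Clinically or statistically significant variables will then be included in subsequent multivariable testing". It gives no p-value for the screen and no list of the variables regarded as clinically important.

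Section 6.4.4, item 1, takes the result into the primary analysis: "Those independently associated with the IMPACT will be reported and factored into the multivariable regression for the primary endpoint". Section 6.4.3 says the same from the other side: "All independent variables that influence IMPACT scores will be controlled for in a multivariable regression model". Section 6.1 describes the adjustment differently, as "controlling for any independent predictors of IMPACT and 15D scores", so predictors of the 15D count there as well.

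Section 6.4 adds that "Effect sizes with 95% confidence intervals (CI) will be provided for every applicable measurement". No section fixes a covariate in advance, controls multiplicity over variables or scores, or labels the predictor search exploratory.

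**The concern.** The same data choose the variables, estimate their effects and supply the intervals, and the procedure is repeated for every module and subscale. Three harms are possible.

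- Secondary objective 1 (section 2.2) asks which factors influence quality of life. Chance associations can pass the screen and be reported as independent predictors, and real but weak effects that pass can be overstated.
- The promised 95% intervals take no account of the selection.
- A screen on marginal association with IMPACT can discard a genuine confounder of the IMPACT-15D relation, because a confounder whose direct effect opposes its path through the 15D may show little marginal association.

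The clinical route into the models does not cure this. The rule joins the two routes with *or*, so a small p-value suffices, and the clinical route is undefined.

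**Working it through.** **Sample size per score (section 6.5).** The plan's figure reproduces: 150 / 0.30 = 500 recruited, and 500 / (1 − 0.33) = 747 invited, against 750 stated. Expected numbers per module are 500 × 0.40 = 200 (nasal), 500 × 0.30 = 150 (orbital), 500 × 0.60 = 300 (jaw) and 500 (general, taken by everyone).

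**Scores (section 5.1.1).** 4 modules + (4 + 2 + 2 + 2) subscales = 14. Three of them (orbital) have n near 150; five (general) have n near 500.

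**Variables (section 6.4.1).** 8 sociodemographic + 11 trauma + 8 management + 4 complication + 3 survey metadata = 34, with presenting signs and repair types counted singly. Repair type as one variable gives 30; grouping the signs too gives 27.

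**Screen alone.** Assume a 0.05 threshold, independent variables and no true effects.

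- 34 variables: 34 × 0.05 = 1.7 false positives per score; 34 × 14 = 476 tests, 23.8 false positives; chance of at least one per score 1 − 0.95^34 = 82.5%.
- 27 variables: 1.35 per score; 378 tests, 18.9 false positives; 1 − 0.95^27 = 75.0%.

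**Screen, then refit (simulation).** 2,000 data sets per setting with normal covariates: univariable screen at 0.05, then least squares on the survivors. A spurious predictor is a noise variable that is still significant at 0.05 after refitting. Coverage is the share of screened-in noise variables whose 95% interval contains zero.

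| n | Variables | True effects | Correlation | At least one spurious | Mean number | Coverage |
|---|---|---|---|---|---|---|
| 150 | 34 | none | 0 | 82% | 1.35 | 21% |
| 500 | 34 | none | 0 | 80% | 1.49 | 11% |
| 150 | 27 | none | 0 | 72% | 1.10 | 16% |
| 500 | 27 | none | 0 | 74% | 1.24 | 10% |
| 150 | 34 | five of 0.15 SD | 0 | 66% | 1.01 | 33% |
| 500 | 34 | five of 0.15 SD | 0 | 65% | 1.03 | 31% |
| 150 | 34 | five of 0.15 SD | 0.2 | 22% | 0.25 | 98% |
| 500 | 34 | five of 0.15 SD | 0.2 | 43% | 0.60 | 98% |

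With four true effects of 0.20 SD, coverage is about 38 to 40% for independent covariates and 95 to 98% for correlations of 0.2 to 0.4.

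**Overstatement (independent covariates).** True effects of 0.20 SD that survive average 0.23 to 0.244 at n = 150, which is 15 to 22% too large (0.23 / 0.20 = 1.15; 0.244 / 0.20 = 1.22). At n = 500 they average 0.199, so there is no overstatement. Weaker effects fare worse: 0.15 SD averages 0.226 at n = 150 (0.226 / 0.15 = 1.51) and 0.158 at n = 500 (1.05).

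**How much is multiplicity.** Entering all 34 variables without a screen still gives 34 × 0.05 = 1.7 false positives per score with no true effects, or 30 × 0.05 = 1.5 with four. Interval coverage in that fixed model is about 95% in every setting.

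**Adjusted IMPACT-15D coefficient.** 3,000 data sets per setting, 34 covariates.

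| Covariates | Selected set, n = 150 | Selected set, n = 500 | Fixed set |
|---|---|---|---|
| Unrelated to 15D | 94–95% | 94–95% | 95% |
| Five confounders, same direction as the 15D effect | 94–95% | 95% | 95–96% |
| Five weaker confounders, opposed | 77% | 50% | 96% |
| Five stronger confounders, opposed | 36% | 2% | 95% |

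In the two opposed settings the bias at n = 150 is −0.08 and −0.155 on a true coefficient of 0.35.

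**The case against.** The strongest reply has four parts.

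*The intervals need not fail.* A reader might infer that the plan's confidence intervals are invalid outright. The documents do not support that. The listed variables overlap by design: CFI and FISS both grade severity, alongside level of care, length of stay and treatment. With positive correlation and true effects, coverage is near or above nominal. Low coverage given selection is also partly built in by conditioning on a small p-value, and it depends on the threshold: with 34 independent noise variables it is 0% at a 0.01 screen, 20% at 0.05, 53% at 0.10 and 76% at 0.20. This part stands. It does not remove the spurious predictors, which appear in every setting.

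*The screen is not the main cause.* An unscreened model of all 34 variables gives as many false positives or more. This stands too, so dropping the screen without dealing with multiplicity would not be enough. Error control could be left to a statistical analysis plan. The selection rule is not left open, though: the protocol prescribes it.

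*The primary verdict may be untouched.* A reader might infer that the validity conclusions are compromised. Section 6.4.3 writes its criterion, significance at 0.05 and "at least moderately-positive correlation" above 0.4, for Pearson's r, and it is unclear whether the unadjusted or the adjusted result decides. If the unadjusted r decides, covariate selection changes no verdict. If the adjusted result decides, failure still needs confounders that act against the 15D effect, and nothing in the protocol shows that these exist.

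*Different covariates per score are not in themselves an error.* The modules cover different regions and patients, and comparison between modules is not a stated objective. This stands.

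**Conclusion.** The concern holds in a conditional form and should be corrected. The protocol prescribes a data-driven choice of covariates for 14 scores, reports the survivors as independent predictors from the same data, and feeds them into the adjusted primary regression.

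- **Firm:** about 0.25 to 1.5 spurious predictors per score and a 22 to 82% chance of at least one, depending on n, covariate correlation and true effects. Part of this is multiplicity that would remain without the screen.
- **Conditional:** intervals for screened-in noise variables are badly anti-conservative only when covariates are close to independent. With independent covariates, 0.20 SD effects are overstated by about 20% at the orbital sample size but not at the general module's.
- **Possible, not shown:** bias in the adjusted IMPACT-15D estimate.

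The figures assume a 0.05 screen, normal covariates, least squares and the expected module sizes in section 6.5. The true correlations and effects are unknown.

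**What to change.** In sections 6.4.1, 6.4.3 and 6.4.4, replace the screen with one short covariate set named before analysis from variables already collected. An example is age, sex, SVI, payor, FISS or CFI, treatment type and time from trauma to survey, with MMF at survey added for the jaw scores. Keep every named covariate whatever its p-value, and use this set as the only adjustment set for the primary regression. Bring section 6.1 into line, since it alone speaks of predictors of the 15D.

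The set is affordable at the smallest module. With six payor categories (5 parameters) and three treatment categories (2), it uses 1 + 1 + 1 + 5 + 1 + 2 + 1 = 12 parameters, or 150 / 12 = 12.5 patients per parameter for the orbital scores.

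Report all other variables as exploratory, with false-discovery-rate control over variables and scores. If named covariates are also to be declared predictors on p-values, bring them under the same control: 7 × 14 + 3 = 101 tests at 0.05 would give about 5 false positives if none mattered.

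The cost is wording only: no new data, patients or visits, provided the set is fixed before the data are analysed. The downside is that a variable outside the list can be reported only as exploratory.

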#### 6.4.2 PROM Scoring

- IMPACT Scoring: IMPACT modules consist of 8-16 Likert scale questions from 0-4 (5-point). The total module score will be standardized by taking the average of all questions in a module then multiplying x25, giving a total module score of 0-100 with higher scores indicating more worse QOL impairment. The pain scale will be reported separately and the final score will be the patients pain score from 0-10 multiplied by 10 for a final pain score of 0-100. For the initial analysis, partially completed surveys with any number of missing answers will be included. Individual subscales for each module will also be given a “subtotal” score which is the average of the Likert scale answers in that subscale, multiplied by 25 for a standardized score from 0-100.
- 15D Scoring: The 15D is scored using a non-linear, copyright algorithm that accounts for baseline demograpic variability. It is available here: <https://15d-instrument.net/15d/> (15D©/Harri Sintonen). The code for this analysis already been released to the host institution for use in the analysis of this study.

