#### **3.2.2 Total Number of Study Sites/Total Number of Subjects Projected**

The study will be conducted at approximately 10 investigative sites across the United States. Recruitment will stop when 150 subjects have completed each IMPACT Module. It is expected that approximately 500 subjects will be enrolled to yield 150 subjects that are indicated for each IMPACT module.

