## 5 STUDY EVALUATIONS AND MEASUREMENTS

### 5.1 Screening and Monitoring Evaluations and Measurements

#### 5.1.1 IMPACT Survey

The IMPACT is a PROM with 4 independent modules. The first is a “General Module” for all patients with maxillofacial trauma. The remaining three modules were designed for specific fractures involving nasal, orbital, and/or jaw regions (Table 1). Each module takes 2-5 minutes to complete for a total of 2-20 minutes/survey depending on fracture pattern.

1. General Module (IMPACT-G)
  - a. **Target patients:** All maxillofacial trauma patients
  - b. **Number of questions:** 21
  - c. **Structure:** 5-point Likert Scales (except for a single “pain score” from 0-10)
  - d. **Subscales (4):** Overall Facial Appearance, Psychosocial Function, General Symptoms, Pain
2. Nasal Module (IMPACT-N)
  - a. **Target patients:** Fractures of the nasal bones and/or sinuses
  - b. **Number of questions:** 15
  - c. **Structure:** 5-point Likert Scales
  - d. **Subscales (2):** Nasal Function, Nasal Appearance
3. Orbital Module (IMPACT-O)
  - a. **Target patients:** Fractures of the orbital walls or rim
  - b. **Number of questions:** 15
  - c. **Structure:** 5-point Likert Scales
  - d. **Subscales (2):** Orbital Function, Orbital Appearance
4. Jaw Module (IMPACT-J)
  - a. **Target patients:** Fractures of the mandible or upper jaw
  - b. **Number of questions:** 20
  - c. **Structure:** 5-point Likert Scales
  - d. **Subscales (2):** Jaw Function, Jaw Appearance

**Table 1:** User guide for the Integrated Modular Patient-Reported Outcome Assessment for Craniomaxillofacial Trauma (IMPACT).

IMPACT Modules	IMPACT-G	IMPACT-N	IMPACT-O	IMPACT-J
Facial Soft Tissue Injury	X			
Upper Facial Third Fractures				
Frontal Sinus	X	X		
Superior orbital rim	X		X	
Middle Facial Third Fractures				
Nasal bones and/or septum	X			
Facial sinus fractures	X	X		
Naso-orbito-ethmoid	X	X	X	
Orbital rim and/or wall	X		X	
Zygomaticomaxillary complex (ZMC)	X		X	X
Zygomatic arch fracture	X			X
Upper dentoalveolar or palate	X			X
Le Fort I	X	X		X
Le Fort II/III	X	X	X	X
Lower Facial Third Fractures				
Mandible	X			X
Lower dentoalveolar	X			X

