### **7.5.2 Risk Assessment**

Risk assessment will be performed by each participating institution. At the host institution, the research activities present were determined to pose no more than minimal risk to human subjects. Potential risks include loss of confidentiality, addressed above, and risk of feeling uncomfortable when taking the survey. This is addressed by ensuring the survey is optional and explaining that some questions may be uncomfortable. Patients may stop the survey at any time or skip items to minimize this risk.

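### Section 6.4.2 sets no minimum number of answered items, so an IMPACT score resting on one or a few answers can carry full weight in the primary correlation

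*Protocol*

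**What the plan says.** Protocol section 6.4.2 (PROM Scoring) gives the inclusion rule: "For the initial analysis, partially completed surveys with any number of missing answers will be included". For modules it says: "The total module score will be standardized by taking the average of all questions in a module then multiplying x25". For subscales the score is one "which is the average of the Likert scale answers in that subscale, multiplied by 25 for a standardized score from 0-100". The section gives no minimum number of answers, no imputation rule and no second analysis under a stricter rule.

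Section 7.5.2 (Risk Assessment) makes incomplete forms likely by design: "Patients may stop the survey at any time or skip items to minimize this risk".

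Section 6.4.3 takes these scores into the primary analysis by "calculating Pearson's r between the score from each IMPACT module and subscale with the 15D QOL survey". A module or subscale is declared valid when p < 0.05 and r > 0.4. Section 6.4.4 uses the scores again for the correlation between initial and follow-up surveys and for the MCID.

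Section 3.2.2 sets the stopping point: "Recruitment will stop when 150 subjects have completed each IMPACT Module". It does not define *completed*.

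The item counts disagree. Section 6.4.2 gives 8 to 16 Likert questions per module. Section 5.1.1 gives 21 for IMPACT-G (one of them the 0–10 pain item), 15 for IMPACT-N, 15 for IMPACT-O and 20 for IMPACT-J.

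**The concern.** The protocol states an inclusion rule with no lower limit, so this is more than a detail left open. Two separate harms follow.

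- **Precision.** A score built on one item can only be 0, 25, 50, 75 or 100, and it carries far more measurement error than a full score. Pearson's r weights both equally. If the sparse answering is random, the error pulls r toward zero and can fail a module that deserves to pass r > 0.4.
- **Meaning.** IMPACT-N, IMPACT-O and IMPACT-J each combine a function and an appearance subscale. A patient who stops partway gets a total that reflects only the items reached. If skipping is selective, the total no longer measures the same thing in every patient, and r can be biased in either direction.

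The validity verdict, the initial/follow-up correlation and the MCID are all exposed, because section 6.4.2 gives the only scoring rule for them. The pain score is a single item by design and is not affected.

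**Working it through.** **The plan's own figures.** Section 6.5 needs 150 patients for IMPACT-O, indicated in 30%: 150 / 0.30 = 500. With 33% nonresponse, 500 / 0.67 = 746.3, so 747; with one third it is exactly 750. Both stated figures reproduce. The protocol gives no power figure for the correlation.

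**What one answer does to a score.** Take 15 items, one answered 4 and fourteen answered 1.
- All answered: (4 + 14 × 1) / 15 × 25 = 30.
- Only the first answered, mean of answers: 4 × 25 = 100.
- Only the first answered, blanks counted as 0: 4 / 15 × 25 = 6.7.

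The same patient scores 30, 100 or 6.7, depending on how much was answered and which denominator is used.

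**Inputs for the effect on r.** From the protocol: 15 items (IMPACT-N and IMPACT-O, section 5.1.1), n = 150 (sections 3.2.2 and 6.5) and the threshold r > 0.4 (section 6.4.3). Assumed, because the protocol does not give them: parallel items with inter-item correlation ρ = 0.4; full-scale r of 0.50 or 0.45; a share s of patients who answer one item at random and also have a scorable 15D.

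**Reliability** of an m-item mean (Spearman-Brown) is mρ / (1 + (m − 1)ρ): 0.40 for 1 item, 0.8 / 1.4 = 0.57 for 2, and 6 / 6.6 = 0.91 for 15.

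**Correlation in the mixed sample.** With item variance 1, an m-item mean has variance ρ + (1 − ρ)/m: 0.4 + 0.6/15 = 0.44 for 15 items and 1 for one item. Its covariance with a standardised 15D is the same for both, 0.50 × √0.44 = 0.3317. Hence r(s) = 0.3317 / √((1 − s) × 0.44 + s × 1).

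**Chance of observed r > 0.4** (Fisher z): Φ[(atanh r(s) − atanh 0.4) × √147].

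| Share answering one item | r (full 0.50) | Chance of r > 0.4 | r (full 0.45) | Chance of r > 0.4 |
|---|---|---|---|---|
| 0% | 0.500 | 94% | 0.450 | 77% |
| 2% | 0.494 | 92% | 0.444 | 74% |
| 10% | 0.471 | 86% | 0.424 | 64% |
| 20% | 0.446 | 75% | 0.402 | 51% |

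For the 0.45 columns the numerator is 0.45 × √0.44 = 0.2985. The 75% is the Fisher approximation; simulation under the same model gives 76%, the figure used in the conclusion.

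**Sensitivity to the assumed consistency.** If Cronbach alpha for the 15 items is 0.8 to 0.9, then ρ = alpha / (15 − 14 × alpha) = 0.21 to 0.375. With full-scale r = 0.50, simulation gives a chance of 72–85% at s = 10% and 50–74% at s = 20%, so the losses are equal or larger.

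**Milder missingness.** If 10% of patients answer 7 of 15 items, the variance of their mean is 0.4 + 0.6/7 = 0.486. Then r = 0.3317 / √(0.9 × 0.44 + 0.1 × 0.486) = 0.497, and the chance is 93%. Near-empty forms do the damage; moderately incomplete ones hardly matter.

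**Effect of a half-items minimum.** If 20% answer 8 of 15, the variance of their mean is 0.4 + 0.6/8 = 0.475. Then r = 0.3317 / √(0.8 × 0.44 + 0.2 × 0.475) = 0.496, and the chance is 93%, against 94% with complete data.

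**The case against.** Several points can fairly be made for the plan.

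- **The module denominator is not fixed.** Only the subscale sentence speaks of answers; the module sentence averages all questions. A reader might infer that the protocol expressly scores a module as the mean of whatever was answered, but it does not. That is the natural reading and matches the subscale rule. The alternative, blanks as zero, would record unanswered items as no impairment and is no better.
- **The rule is tied to an initial analysis.** This suggests a later, stricter one, which a statistical analysis plan might contain. It stands as a caution. But section 6.4.3 names no other scores, and an inclusion rule without a lower limit is a stated choice.
- **Near-empty forms may not count toward the 150.** A reader might infer that they do. No text says so. Section 6.4.2 has a separate term for partial forms, and the ordinary meaning of *completed* excludes them. What stands is that the word is undefined.
- **A form enters r only with a 15D score.** A patient who leaves 14 of 15 module items blank may leave no usable 15D either. Survey order and the handling of missing 15D answers are not stated. This objection stands and limits the size.
- **Shares of 10–20% are assumptions.** Nothing in the protocol suggests that one-item forms are that common, and at 2% the loss is slight. Random sparse answering also works against declaring validity. Both points stand, though selective skipping need not be conservative.

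**Conclusion.** The concern holds as a weakness in a stated scoring rule that should be corrected. Section 6.4.2 admits forms however incomplete, section 7.5.2 permits skipping and stopping, and section 6.4.3 uses the resulting scores for the validity verdict with no other rule on offer.

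The size is uncertain. With 15 parallel items, inter-item correlation 0.4, full-scale r of 0.50 and n = 150, the chance of passing r > 0.4 falls from 94% to about 92%, 86% or 76% when 2%, 10% or 20% of patients answer a single item and also supply a scorable 15D. The loss is larger if the full-scale r lies nearer the threshold or internal consistency is lower, and negligible if near-empty forms are rare. The effect of selective skipping cannot be quantified from the protocol.

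A reader might infer that the primary result is bound to be distorted. The protocol does not support that, because it gives no share of near-empty forms.

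**What to change.** 1. **Section 6.4.2, subscales.** Score a subscale as the mean of answered items times 25 only when at least half of its items are answered; otherwise set it to missing. One half is a convention, and nothing in the protocol derives it.
2. **Section 6.4.2, modules.** Score a module total only when each of its multi-item subscales meets that rule, and state the denominator. A half-of-module rule would not suffice: if a 15-item module splits 8 and 7, a patient who answers only the first subscale has 8/15 = 53% and would still get a total. (The split is illustrative; section 5.1.1 does not give it.)
3. **Sensitivity analysis.** Keep the present all-forms version in this role.
4. **Section 3.2.2.** Define *completed* for the count of 150 by the same rule.
5. **Item counts.** Reconcile 8–16 in section 6.4.2 with 15–21 in section 5.1.1, because the minimum depends on them.

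The cost is a few sentences. Some near-empty forms leave the main analysis, and the 150 may be reached slightly later. If a share q of IMPACT-O forms falls below the minimum and must be replaced, recruitment becomes 150 / (0.30 × (1 − q)): 511 at q = 2% and 556 at q = 10% (both assumed), against 500. If *completed* was already meant to exclude such forms, the rule adds nothing to what was intended.
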